2.0 OBJECTIVES

Primary

- To improve the accuracy of hypoxia imaging for head and neck cancers through pixel by pixel kinetic analysis of ^{18}F -FMISO tracer of dynamic PET images (Cohort 1 and Cohort 2).
- To detect on repeat ^{18}F -FMISO PET/CT scans whether there is a reduction of the ^{18}F -FMISO-avid or GIV_h 5 to 10 days into treatment with standard chemoradiotherapy for a series of locally advanced head and neck cancers (Cohort 1).
- To show that it is feasible to deliver 70Gy to primary site and 60Gy to the neck nodes in HPV+ patients who exhibit no evidence of hypoxia on their baseline ^{18}F -FMISO PET/CT scans or those who have early resolution of hypoxia on their early repeat ^{18}F -FMISO PET/CT scans (Cohort 1).
- To show that it is feasible to deliver 30Gy to the surgical bed and neck nodes in low-risk HPV+ patients who exhibit no evidence of hypoxia on their repeat ^{18}F -FMISO PET/CT (Cohort 2).
- To correlate the intensity of the ^{18}F -FMISO PET signal with the degree of immunohistochemical staining of hypoxia biomarkers for tissue obtained via biopsy (Cohort 1) and surgical resection (Cohort 2): HIF-1 α , Lysyl Oxidase, and Ki67 (an independent marker of tumor aggressiveness), among others.

Secondary

- To compare tumor heterogeneity derived from pixel-by-pixel kinetic analysis of PET scan and DWI-MRI (Cohort 1).
- To assess changes in tumor heterogeneity over the course of external beam RT using serial multiparametric MR and DCE-MRI scans (Cohort 1).
- To determine the potential of DCE-MRI data as a priori or early markers of tumor response to chemoradiation as well as long term disease-free survival after treatment (Cohort 1).
- To assess normal tissue response as a function of dose for parotid, submandibular glands, muscles and bones in the head and neck region during and after EBRT using serial multiparametric MR scans (Cohort 1).
- To bank specimens for further IRB/PB approved exploration of genetic analysis (Cohort 1 and Cohort 2).

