This is the first human study that uses a non-invasive imaging technique for hypoxia (^{18}F -FMISO PET/CT) for the purposes of immunohistochemistry (IHC) correlation for tissue markers of hypoxia. To date, nearly 20 biopsy specimens have been obtained on this protocol where an interventional radiologist biopsied areas that demonstrated high ^{18}F -FMISO uptake on the ^{18}F -FMISO PET/CT scan. However, initial results from these biopsies have demonstrated that nearly 50% of these specimens did not contain tumor cells, despite being obtained from both FDG avid and ^{18}F -FMISO avid regions. Only stromal, fibrous, and lymphoid tissues were able to be identified. In order to overcome the sampling error associated with small needle biopsy, we will obtain more tumor tissue without deviating from current standards of care for head and neck cancer. Given that one current standard in the treatment of loco-regionally advanced oropharyngeal cancer is surgical resection using the robotic surgery technique, we plan to utilize the surgical specimens of these patients for our IHC hypoxia studies. Furthermore, we will image these patients with an ^{18}F -FMISO PET/CT scan prior to their standard of care pretreatment surgical resection in order to correlate hypoxia on imaging with IHC performed on their surgical specimen. The surgeons performing these surgical resections will be asked to orient their surgical specimen according to the ^{18}F -FMISO PET/CT. Patients undergoing this standard of care surgical resection will make up Cohort 2 of this protocol.

In summary, we will perform the first human study of ^{18}F -FMISO PET image-guided core biopsy of neck node(s) in both HPV positive and negative HNSCC (for Cohort 1 patients that consent to this optional biopsy). Additional tissue will be collected from patients who will undergo surgical resection of their HNSCC per standard of care (Cohort 2). We will correlate the intensity of the ^{18}F -FMISO PET signal with the degree of IHC staining of the following hypoxia biomarkers, among others: HIF-1 α , Lysyl Oxidase, and Ki67 (an independent marker of tumor aggressiveness).

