For Cohort 1 main campus patients, the follow-up MR scans, which will occur during concurrent chemoradiation, will last approximately 20-40 minutes. Information collected from all MR scans will not affect the standard of care, as baseline and post-treatment scans are currently a component of the standard of care. Additional scans will be acquired on our Philips 3T research scanner. Images will be sent to the research Pinnacle workstation for storage and evaluation. These images may be used for contouring of normal structures during the treatment planning process. DW-MRI images will be processed on the Philips research platform and corresponding diffusion and perfusion maps will be analyzed for therapy response assessment and treatment planning. Spatial changes during treatment will also be evaluated using functional diffusion maps or parametric response maps. No clinical decision will be made at this point based on MR findings.

PET/CT Image-guided Core Biopsy (Optional – Cohort 1 Patients Only)

The PET/CT scan will be performed in the Center for Image-Guided Intervention and Surgery at MSKCC, which houses a PET/CT scanner in an interventional radiology and operating room environment. The PET image-guided core biopsy procedure will be conducted as follows:

On the day of ^{18}F -FMISO PET/CT imaging, patients will be injected with the study tracer, ^{18}F -FMISO. After the final ^{18}F -FMISO PET image acquisition at each visit session (where applicable), biopsy samples will be removed from tumor tissue exhibiting high and low ^{18}F -FMISO uptake (if both are available). These high and low ^{18}F -FMISO uptake regions correspond to putative hypoxic and normoxic regions, respectively. Parametric image maps will also be retrospectively generated from compartmental models that define the rate of ^{18}F -FMISO radiotracer entrapment. These values will be used, in addition to the percent injected dose per gram, for correlation with IHC of hypoxia specific markers.

The aforementioned biopsy samples will be obtained by an interventional radiologist according to the features of the ^{18}F -FMISO PET/CT images. 1% lidocaine will be used for local anesthesia supplemented with midazolam and fentanyl citrate for light conscious sedation. The biopsy needle will be placed in position to remove core biopsy material of the node(s), and the patient will have an additional low dose CT to visualize the biopsy

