needle trajectory and location. In this way, we will obtain information of the exact location of the biopsy specimen in regard to the CT and therefore co-registered PET image. If movement should occur between biopsy localizer CT and the CT attenuation scan, then these two CT images will be co-registered using mutual information density software. Immediately following biopsy, the specimen will be properly oriented and pinned. Based upon published experience, discussion with other investigators, and our own experience of obtaining tissue prior and during treatment, we anticipate it will take approximately fifteen minutes to perform each biopsy. The specimen acquired from these tumor samples will be taken for paraffin embedding, fresh frozen (if patient consents to any of optional banking studies), and histological processing to our Pathology Department. Ten 5 μ m thick sections from paraffin tumor blocks or core samples will be deparaffinized and rehydrated, and stored at -80 °C until processing. IHC analyses will also be performed for the following hypoxia relevant biomarkers, among others: HIF-1 α , LOX, and Ki-67.

Pretreatment Surgical Resection (Cohort 2 Patients Only)

The eligible patient will undergo a pre-surgery FDG PET scan and an ¹⁸F-FMISO PET/CT scan. Following these pre-surgical scans, the patient will undergo his/her standard of care surgery. The surgeon will annotate the location of each sample resected from the lesion by a text description for documentation of relative position. The specimen will be embedded in paraffin in an orientation that will allow sectioning parallel to the imaging plane of the PET/CT image. Tissue sections will be stained with H&E, hypoxia specific, and proliferation markers using the same procedures as the described for the biopsy specimens in this protocol.

Biospecimen Samples

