100 HPV+ patients with negative baseline scan or early resolution of tumor hypoxia of their node(s) at 5-10 treatment days into chemoradiation, defined by an absence or disappearance of ^{18}F -FMISO uptake on PET/CT, will achieve an equivalent nodal control with nodal radiation dose at 60Gy in the setting of chemotherapy with concomitant reduction in treatment-related complications. To test if patients receiving 60Gy to the node(s) followed by an FDG PET and observation similar treatment outcomes when compared to the radiation of 70Gy to the nodes both in the setting of concurrent chemotherapy, we will apply a one-sided one sample proportion test. Our past experience is that the nodal control rate at 3 months for such patient with 70Gy to the nodes is 94%. We will reject our hypothesis of equivalent control whether patients receive 70Gy to the nodes or 60Gy to the nodes followed by an FDG PET and observation if ≤ 57 patients out of the 66 in total who received 60Gy to the nodes achieve the same 3-month nodal control after chemoradiation. With this rule, we have a power of 0.93 for detecting that 60Gy will result in 3-month regional control lower than 80% with the type I error rate lower than 0.05. To test if patients receiving 60Gy to the nodes followed by an FDG PET and observation show superior toxicity outcomes when compared to the historical results from similar patients receiving 70Gy, we will apply a one-sided one sample proportion test. Grade 2 or higher toxicities that occurred within 3 months from the completion of IMRT will be counted in this analysis. Our past experience is that this toxicity rate for patients receiving 70Gy is around 75%. Using the total of 66 patients that undergo 60Gy to the nodes, we will reject our hypothesis of equivalent or higher toxicity rate when the nodes receive 10Gy less radiation from 70Gy when ≤ 43 patients have at least one \geq grade 2 toxicities. With this rule, we have a power of 0.84 for detecting the probability of 60% of patients will have at least one \geq grade 2 toxicity with the type I error rate lower than 0.05. Effort will be made to monitor all toxicities occurring beyond 3 months from chemotherapy and IMRT for all patients. However, censoring can be an issue so we will not apply the proportion test for toxicities after 3 months from chemoradiation. Instead, we will summarize the data descriptively and when applicable, we will use survival analysis tools such as Kaplan-Meier estimation and log-rank tests to determine whether 60Gy results in lower toxicity. To examine the potential correlations between various evaluation methods for nodal control status, we will apply a series of Fisher's exact tests.

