
The spatial extent of ^{18}F -FMISO PET imaging within the neck node(s) determines the underlying hypoxia tumor phenotype for both HPV positive and negative HNSCC. To determine whether baseline ^{18}F -FMISO PET/CT and/or early-response ^{18}F -FMISO PET/CT at 5-10 treatment days after chemotherapy and IMRT correlate with selected proliferative/hypoxia molecular markers, Wilcoxon rank sum tests will be used for each marker. Multiple testing adjustments such as Bonferroni procedures will be used. To investigate whether the extent of ^{18}F -FMISO PET/CT measured hypoxia at baseline and/or 5-10 treatment days into chemoradiation for both HPV positive and negative tumors correlates with the development of distant metastasis, Kaplan-Meier estimates will be calculated for each stratum and compared using the log-rank tests. When competing risks are present, Gray's test will be used to examine the correlation between the extent of ^{18}F -FMISO PET/CT measured hypoxia with the development of distant metastasis. To examine the potential correlations between the baseline and early

response ¹⁸F-FMISO PET imaging and tumor's underlying HPV status, we will apply Fisher's exact tests.

Multiparametric scans will also be obtained. We will attempt comparisons to ¹⁸F-FMISO PET results and immunohistochemistry hypoxia results, but due to the small pilot size of this exploratory aim, we may not produce significant results. In that case, we will present summary statistics and suggest directions for future study.

> For this study cohort, 14 eligible patients will be needed for the analysis. Assuming approximately 25% of the patients enrolled will not be eligible, we will plan to recruit 19 patients upfront. For evaluation on the efficacy of the regimen in this cohort, a simple decision rule will be implemented, which is as follows: If, among the total 14 eligible patients, we have at least 10 patients who are alive, followed and have a pathologic CR at 4 months from the end of the treatment, then we will declare the treatment modality using 30 Gy is feasible and worthy of further investigation. Any patient who died or is lost to follow up within 4 months from the end of radiotherapy will be regarded as a failure, i.e., without pathologic CR. Feasibility for the primary objective in cohort 2 will be defined according to aforementioned decision rule. This decision rule has the following probabilities of declaring success.

True Locoregional Control Rate									

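### For the marker tests, name Holm's step-down procedure in place of Bonferroni (now only an example) and list the tests it covers: same error control, never less power

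*Combined protocol and SAP*

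**What the plan says.** Section 2.0 (Objectives) lists the correlation of FMISO signal with immunohistochemical staining among the primary objectives, for biopsy tissue in Cohort 1 and surgical tissue in Cohort 2. HIF-1 alpha is named first, and the list ends "Lysyl Oxidase, and Ki67 (an independent marker of tumor aggressiveness), among others". Section 4.1 (Design) names the same three markers and leaves the list open in the same way: "IHC analyses will also be performed for the following hypoxia relevant biomarkers, among others".

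Section 14.0 (Biostatistics) gives the analysis: "selected proliferative/hypoxia molecular markers, Wilcoxon rank sum tests will be used for each marker". It does not list the selected markers. The imaging side is baseline "PET/CT and/or early-response" scan, so one or two time points. On multiplicity it says only: "Multiple testing adjustments such as Bonferroni procedures will be used".

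Section 4.1 also brings in more than one uptake measure. Of the compartmental-model values it says: "These values will be used, in addition to the percent injected dose per gram, for correlation with IHC of hypoxia specific markers".

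No alpha or sidedness is given for the marker tests. The phrase "with the type I error rate lower than 0.05" belongs to the one-sample proportion tests of nodal control and toxicity.

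**The concern.** There are two linked points, and the first carries the recommendation.

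First, the only procedure mentioned is dominated by another. Holm's step-down procedure keeps the family-wise error at the same level, needs no extra assumption about dependence between tests, and rejects every hypothesis that Bonferroni rejects and sometimes more. Tissue is limited: Section 3.0 reports that in the early biopsies "nearly 50% of these specimens did not contain tumor cells". Power that costs nothing is worth taking.

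Second, any such correction needs a known number of tests, and the plan does not fix one. The markers, the scans and the uptake measures can each change the count. If the count is settled after the results are seen, the corrected p-values no longer have a defined error rate. If every possible test is counted, the three named markers face a stricter threshold than they need to.

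**Working it through.** **Stated figure.** The plan gives no sample size, power, alpha or number of tests for the marker analysis, so there is nothing to reproduce. The neighbouring figures in Section 14.0 do reproduce from the binomial distribution. The nodal rule (57 or fewer of 66) has type I error 0.017 at 94% and power 0.932 at 80%; the plan states below 0.05 and 0.93. The toxicity rule (43 or fewer of 66) has 0.048 at 75% and 0.836 at 60%; the plan states below 0.05 and 0.84. All nine entries of the Cohort 2 table (10 or more of 14) match to three decimals.

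**Inputs.** From the documents: three named markers, one or two scans, at least two uptake measures. Assumed, because the documents do not say: family-wise alpha 0.05, two-sided; unadjusted power of 30%, 50% or 80% per true effect; normally distributed test statistics, independent unless stated.

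**Thresholds.** Bonferroni tests all m hypotheses at 0.05/m. Holm orders the p-values and compares the i-th smallest with 0.05/(m − i + 1), stopping at the first failure.
- m = 3: Bonferroni 0.0167 for each; Holm 0.0167, 0.025, 0.05.
- m = 6: Bonferroni 0.0083 for each; Holm 0.0083 rising to 0.05.

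The first Holm step equals Bonferroni, so Holm can add only second and later rejections.

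**Bonferroni power in closed form.** Power ≈ Φ(z₀.₉₇₅ + z_power − z_crit). At 80% unadjusted power the shift is 1.960 + 0.842 = 2.802.
- m = 3: Φ(2.802 − 2.394) = 0.658
- m = 6: Φ(2.802 − 2.638) = 0.565
- m = 12: Φ(2.802 − 2.865) = 0.475

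**Holm against Bonferroni by simulation** (400,000 replicates; average power per true effect):

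| Tests | True effects | Unadjusted power | Bonferroni | Holm |
|---|---|---|---|---|
| 3 | 3 | 80% | 0.66 | 0.75 |
| 3 | 3 | 50% | 0.33 | 0.38 |
| 3 | 3 | 30% | 0.17 | 0.19 |
| 3 | 2 | 80% | 0.658 | 0.696 |
| 3 | 1 | 80% | 0.660 | 0.661 |
| 6 | 6 | 80% | 0.565 | 0.683 |
| 12 | 3 | 80% | 0.47 | 0.48 to 0.49 |

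With three true effects at 80% and correlation 0.5, the figures are 0.658 and 0.735. The chance of at least one rejection with three true effects at 80% is 0.960 for both methods. In the three- and six-test settings checked replicate by replicate, Holm rejected everything that Bonferroni rejected. Its family-wise error stayed at or below about 0.049, and under the global null the two methods had the same error (0.049 for m = 3 and m = 6).

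**Error if the divisor does not match the tests run.** With each test at 0.05/3 and k independent true nulls, family-wise error = 1 − (1 − 0.05/3)^k.
- k = 3: 0.049
- k = 6 (3 markers × 2 scans): 0.096
- k = 12 (3 markers × 2 scans × 2 measures): 0.183

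**The case against.** The strongest reply is that the plan does not commit to Bonferroni. The wording gives an example, so Holm is already allowed and nothing in the plan is invalid. That stands. A reader might infer that the plan imposes a needlessly blunt correction; the text does not support this. What remains is that the one procedure it mentions is dominated, and that the choice is still open when the data arrive.

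A second reply is that the gain is modest and depends on assumptions. This also stands. Under the most favourable case shown for three tests (three true effects at 80% power, independent tests), the chance of rejecting all three is 0.287 with Bonferroni and 0.495 with Holm. It is tempting to headline that contrast. But no section makes success on all three markers a criterion, the documents give no effect sizes, and 80% power sits uneasily with scarce tissue.

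A third reply is that Holm does not cure a large family. Correct: with 12 tests and three true effects the two methods are almost level, and the loss comes from the number of tests. Section 14.0 also does not say that scans and uptake measures share one divisor, so 12 is a possible reading of the family, not a stated one.

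One might go further and say that the plan must restrict the family to the baseline scan and leave everything else uncorrected. The documents do not support that. Section 14.0 allows baseline, early-response or both scans and promises adjustment; dropping either is a trade-off for the investigators. Nor can it be said that lost power is beyond recovery through more tissue: Section 3.0 adds the Cohort 2 surgical specimens in order to obtain more tumour tissue.

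**Conclusion.** The point holds as a minor improvement. That Holm has the same family-wise control under any dependence and is never less powerful is a mathematical fact and needs no assumption about this trial. The size of the gain does rest on assumptions. With three tests, three true effects and independence, average power rises by about 0.09 at 80% unadjusted power, about 0.05 at 50% and about 0.02 at 30%. With a single true effect it hardly changes, and the chance of at least one finding is essentially unchanged.

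Listing the family matters for error control. The figures of about 0.10 and 0.18 assume independent tests, all null, with a divisor of 3 kept while 6 or 12 tests are run. They show what the open wording would permit; nothing in the documents says that the investigators intend this.

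The severity is minor because no sample size, decision rule or treatment assignment depends on the marker tests. It still deserves a sentence because the correlation is listed as a primary objective.

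**What to change.** Before the marker analysis, replace the multiplicity sentence in Section 14.0 with one along these lines: *The tests of HIF-1 alpha, LOX and Ki-67 against [named uptake measure] on [named scan or scans] form one family and will be adjusted by Holm's step-down procedure at a two-sided family-wise level of 0.05. Tests of other markers, scans or uptake measures will be labelled exploratory, or will form a second family with its own Holm correction.*

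The investigators should fill in the scan or scans and the uptake measure, since Sections 2.0 and 14.0 do not limit the objective to one time point. If both scans enter, the family has six tests and Holm starts at 0.0083 in place of 0.0167.

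The switch to Holm costs nothing in error control and changes no patient procedure. It gives no simple simultaneous confidence intervals, but Section 14.0 promises none for these tests. Listing the family has one real cost: the investigators must choose the scan and uptake measure in advance and accept that tests outside the list carry less weight.

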15.0 SUBJECT REGISTRATION AND RANDOMIZATION PROCEDURES

15.1 Research Participant Registration

Confirm eligibility as defined in the section entitled Inclusion/Exclusion Criteria. Obtain informed consent, by following procedures defined in section entitled Informed Consent Procedures. During the registration process registering individuals will be required to complete a protocol specific Eligibility Checklist. The individual signing the Eligibility Checklist is confirming whether or not the participant is eligible to enroll in the study. Study staff are responsible for ensuring that all institutional requirements necessary to enroll a participant to the study have been completed. See related Clinical Research Policy and Procedure #401 (Protocol Participant Registration).

15.2 Randomization

Not applicable.

16.0 DATA MANAGEMENT ISSUES

A Research Study Assistant (RSA) will be assigned to the study. The responsibilities of the RSA include project compliance, data collection, abstraction and entry, data reporting, regulatory monitoring, problem resolution and prioritization, and coordinate the activities of the protocol study team.

The data collected for this study will be entered into a secure database. Source documentation will be available to support the computerized patient record. All research material from this study will be handled with the same confidentiality as patient's other medical data.

